## 9. BIOLOGICAL SPECIMENS AND CORRELATIVES

### 9.1 Preparation, Shipment and Storage of Specimens

See Study Procedure Manual for collection, processing and shipping instructions for all tissue and blood specimens.

## 10. STUDY DRUG INFORMATION

### 10.1 Study Drug Name

[figure not shown]
Tazemetostat (Tazverik, Epizyme)

#### 10.1.1 Identification

Tazverik is a methyltransferase inhibitor indicated for the treatment of adults and pediatric subjects aged 16 years and older with metastatic or locally advanced epithelioid sarcoma, a rare slow-growing type of soft tissue cancer, who are not eligible for complete resection. Tazemetostat is taken orally, with or without food. Swallow the tablet whole and do not crush, chew or break it.

Chemical Name: [1,1'-Biphenyl]-3-carboxamide, N-[(1,2-dihydro-4,6-dimethyl-2-oxo-3-pyridinyl)methyl]-5-[ethyl(tetrahydro-2H-pyran-4-yl)amino]-4-methyl-4'-(4-morpholinylmethyl)-,hydrobromide(1:1).

Chemical Structure:

Molecular Formula: C34H44N4O4·HBr

Molecular Weight: 653.66 g/mol

Physical Description: Tazemetostat hydrobromide is a white to off-white solid that is slightly soluble in water. Tazemetostat tablets contains 200 mg Tazemetostat, equivalent to 228 mg Tazemetostat hydrobromide. Each Tazemetostat tablet is film-coated, red, round, biconvex shape, and debossed with "EZM 200" on one side and plain on the other.

#### **10.1.2 Packaging and Labeling**

Study drug is provided in bottles of 240 tablets with a desiccant; NDC 72607-100-00.

All study treatment supplies must be stored in accordance with the storage and handling manual instructions and package labeling. Until dispensed to subjects, the study treatment will be stored in a securely locked area, accessible to authorized staff only.

#### **10.1.3 Drug Supply**

The Sponsor Epizyme (or designee) will ship Study Drug to the investigational site, University of Florida. The initial study drug shipment will be shipped after site activation (i.e., all required regulatory documentation has been received by the Sponsor and a contract has been executed). Subsequent study drug shipments will be made after site request for resupply.

#### **10.1.4 Storage, Handling and Dispensing**

##### **Tablets**

Do not store Tazverik tablets above 86°F (30°C). Drug is administered orally, with or without food. Swallow tablets whole; do not cut, crush, or chew. Store at room temperature away from moisture and heat. Keep the tablets in their original container, along with the packet or canister of moisture-absorbing preservative.

##### **Powder suspension**

Do not store above 25°C (77°F). Protect from light. Once oral suspension is prepared, store refrigerated between 2-8 °C (36-46 °F) and protect from light. Brief excursion (less than 4 hours) up to 30°C is allowable for transfer from the clinic to home, but bottles must be immediately refrigerated upon arrival. A cold pack may be provided to the patient as required.

If a storage temperature excursion is identified, promptly return tazemetostat un-reconstituted powder for oral suspension to below 25°C (77°F) and prepared oral suspension to 2-8°C (36-46 °F) and quarantine the supplies.

Drug doses should be adjusted based on the BSA calculated from height and weight measured within 7 days prior to the beginning of each cycle. Shake the bottle for one minute before you take tazemetostat; do not shake too much (if there are bubbles wait for them to dissipate before measuring the dose). Note: If multiple bottles are dispensed, daily shaking of all bottles is required to ensure the suspension stays properly suspended. Store your oral suspension in the refrigerator.

**Table 4. Suspension preparation guidance table**

Total tazemetostat required	2 gm bottles	7 gm bottles	Ora-Sweet® volume* (mL)	Allowable medication bottle size** (mL)
< 2 grams	1	0	65	100-150
2 to < 4 grams	2	0	130	200-300
4 to < 6 grams	3	0	195	250-500
6 to < 7 grams	0	1	228	250-500
7 to < 9 grams	1	1	293	400-700
9 to < 11 grams	2	1	358	400-800
11 to < 12 grams	3	1	[contact]
12 to < 14 grams	0	2	[contact]
14 to < 16 grams	1	2	[contact]
18 to < 20 grams	3	2	[contact]
20 to < 21 grams	0	3	[contact]
21 to < 23 grams	1	3	748	1000-1800
23 to < 25 grams	2	3	813	1000-2000
25 to < 27 grams	3	3	878	1100-2100
27 to < 28 grams	0	4	910	1200-2400

UF-SC-001

2024-Aug-12

28 to < 30 grams	1	4	975	1300-2500
30 to < 32 grams	2	4	1040	1400-2600
32 to < 34 grams	3	4	1105	1500-2800

This table is for guidance purposes only, larger volumes should be calculated using the [Tazemetostat Oral Suspension Preparation Worksheet](#).

\*The volume of Ora-Sweet® to obtain a concentration of 30 mg tazemetostat/mL of suspension accounts for the volume of tazemetostat in the solution.

\*\* Total volume listed may require more than one medication bottle to accommodate. Each medication bottle must be prepared separately but multiple whole bottles of tazemetostat powder for oral suspension can be combined into one medication bottle.

#### 10.1.5 Contraindications

None

#### 10.1.6 Special Warnings and Precautions for Use

Secondary Malignancies: TAZVERIK increases the risk of developing secondary malignancies, including T-cell lymphoblastic lymphoma, myelodysplastic syndrome, and acute myeloid leukemia.

Embryo-Fetal Toxicity: Can cause fetal harm. Advise subjects of potential risk to a fetus and to use effective non-hormonal contraception.

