- Women of childbearing potential (WOCBP) who are heterosexually active must be using two highly effective methods of contraception to avoid pregnancy throughout the study and for at least 6 months after the last dose of study drug to minimize the risk of pregnancy as Tazemetostat might counteract the effects of hormonal contraceptives. Birth control methods that can be used while in this study include: established use of oral, injected or implanted hormonal birth control or placement of an intrauterine device [IUD] or intrauterine system [IUS]. They or their partner must also use a second method, (e.g., condom with spermicidal foam/gel/film/cream/suppository or occlusive cap [diaphragm or cervical/vault caps] with spermicidal foam/gel/film/cream/suppository. If their male partner is vasectomized, they do not need to use any of the birth control methods listed above. The type of birth control they use must be discussed with the study doctor before beginning the study. The study doctor must approve the method you use before they can enter the study. Prior to study enrollment, women of childbearing potential must be advised of the importance of avoiding pregnancy during trial participation and the potential risk factors for an unintentional pregnancy.
- Males with female partners of child-bearing potential must agree to use physician-approved contraceptive methods (e.g., abstinence, condoms, vasectomy) throughout the study and should avoid donating sperm, for 90 days following the last dose of study drug.

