#### 4.3 Exclusion Criteria

Subjects with any of the following present at time of enrollment will not be eligible for study participation:

- A. Subjects who are currently taking the following concomitant medications:
  - Anti-cancer Agents: Subjects who are currently receiving other anti-cancer agents are not eligible.
  - CYP3A4 Agents: Subjects who are currently receiving drugs that are strong inducers or strong inhibitors of CYP3A4 are not eligible. Strong inducers or inhibitors of CYP3A4 are prohibited from 14 days prior to the first dose of Tazemetostat to the end of the study. Note: Dexamethasone for CNS tumors or metastases, on a stable dose, is allowed.
  - Grapefruit, grapefruit juice, Seville oranges and food/drinks containing them should be avoided one week before the first dose of the study intervention
- B. Subjects who are acutely ill with an uncontrolled active infection on systemic anti-infective agents are not eligible.

- C. Subjects with a prior history of T-LBL/T-ALL, myelodysplastic syndrome (MDS), acute myeloid leukemia (AML), B-cell acute lymphoblastic leukemia (B-ALL), or other myeloproliferative neoplasm (MPN).
- D. Subjects who have any of the following underlying major cardiac issues or conditions:
  - Known QTc prolongation or documentation
  - Documented New York Heart Association (NYHA) Class III or IV congestive heart failure.
  - Myocardial infarction within 6 months prior to registration.
  - Unstable angina within 6 months prior to registration.
  - Symptomatic arrhythmia.
- E. Subjects who in the opinion of the investigator may be high risk for treatment complications or unable to comply with the safety monitoring requirements of the study are not eligible.
- F. Heterosexually active males or females of reproductive potential may not participate unless they have agreed to use two highly effective contraceptive methods for the duration of study treatment as Tazemetostat might counteract the effects of hormonal contraceptives. Female subjects of childbearing potential should agree to remain abstinent or use adequate contraceptive methods for 6 months after the last dose of Tazemetostat. Male subjects should agree to remain abstinent or use adequate contraceptive methods, and agree to refrain from donating sperm, and for 90 days after the last dose of Tazemetostat.

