- G. Females who are pregnant or breastfeeding will not be entered on this study because there is currently no available information regarding human fetal or teratogenic toxicities. Pregnancy tests must be obtained in girls who are post-menarchal.
- H. Administration of a vaccine containing live virus within 30 days prior to the first dose of trial treatment. For examples, See Section 7.3.3: Prohibited Concomitant Therapy. **Note:** Most flu vaccines are killed viruses, with the exception of the intra-nasal vainer (Flu-Mist) which is an attenuated live virus and therefore prohibited for 30 days prior to first dose. Patients may receive non-live versions of the COVID-19 vaccine.
- I. Prisoners or subjects who are involuntarily incarcerated, or subjects who are compulsorily detained for treatment of either a psychiatric or physical illness.

- J. Known hypersensitivity to tazemetostat or any component of the formulation of tazemetostat
- K. Inability to take oral medication OR have malabsorption syndrome or any other uncontrolled gastrointestinal condition (eg, nausea, diarrhea, vomiting) that might impair the bioavailability of tazemetostat

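### The contraception rules in Inclusion J, Exclusion F and Section 10.1.6 conflict on four points and are open to different application

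*Combined protocol and SAP*

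**What the plan says.** Contraception and fetal risk are addressed in four places in the protocol. The three eligibility criteria are also repeated in the synopsis.

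- **Section 4.2, Inclusion J, women.** Heterosexually active women of childbearing potential "must be using two highly effective methods of contraception to avoid pregnancy throughout the study and for at least 6 months after the last dose". The reason given is that the drug may weaken hormonal contraceptives. The permitted first methods nevertheless include "established use of oral, injected or implanted hormonal birth control", with an intrauterine device or system as the alternative. A second method, such as a barrier with spermicide, must be added, and the study doctor must approve the choice before entry. There is one waiver: "If their male partner is vasectomized, they do not need to use any of the birth control methods listed above".
- **Section 4.2, Inclusion J, men.** Men whose partners could conceive "must agree to use physician-approved contraceptive methods (e.g., abstinence, condoms, vasectomy"), with no number of methods stated.
- **Section 4.3, Exclusion F.** Heterosexually active men and women of reproductive potential "may not participate unless they have agreed to use two highly effective contraceptive methods for the duration of study treatment". F gives the same reason about hormonal contraceptives, but it names no qualifying methods and has no waiver for a vasectomized partner. After the last dose it asks for abstinence or adequate contraception, for 6 months in women and 90 days in men.
- **Section 4.3, Exclusion G.** Pregnant or breastfeeding women are excluded because "there is currently no available information regarding human fetal or teratogenic toxicities".
- **Section 10.1.6.** "Embryo-Fetal Toxicity: Can cause fetal harm". It then gives the advice on non-hormonal methods: "Advise subjects of potential risk to a fetus and to use effective non-hormonal contraception".

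Section 3.1 enters only subjects who meet every inclusion criterion and no exclusion criterion. Section 4 allows no exceptions. Section 5 has a project manager verify eligibility from a checklist before enrollment.

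**The concern.** The protocol gives different instructions on the same question, depending on where the reader looks. In a trial that admits no eligibility exceptions, a clinician who counsels from Inclusion J can tell a subject that a method is acceptable when Exclusion F then bars that subject. A clinician who counsels from Section 10.1.6 would give different advice on hormonal methods from one who reads J. The drug carries a fetal-harm warning and enrollment starts at age 12, so what is at stake is consistent embryo-fetal protection and consistent screening decisions.

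The issue does not end at enrollment. Section 7.3 makes each new 28-day cycle conditional on remaining eligible under Sections 4 and 7, the Investigator Brochure and the package insert. The conflicting text is thus reapplied for up to 26 cycles (Section 7.2).

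**Working it through.** No formula applies and the plan states no figure on this point. The check sets the passages side by side and asks what each rule returns for a given subject.

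| Subject | Inclusion J | Exclusion F | Result |
|---|---|---|---|
| Man, heterosexually active, condoms alone, physician approves | Met | Barred: two highly effective methods required on treatment | Conflict |
| Woman, vasectomized partner, no listed method | Met through the waiver | Barred: no waiver | Conflict |
| Woman, within 6 months after last dose, adequate contraception that falls short of two highly effective methods | Not met | Post-treatment clause met | Conflict |
| Woman, oral hormonal method plus barrier with spermicide | Met if the study doctor approves | Not settled: F names no qualifying methods | Conflicts with Section 10.1.6 |
| Woman, intrauterine device plus barrier | Met if the study doctor approves | No hormonal or vasectomy question arises | None of the conflicts above |
| Abstinent man | Met | F does not apply: not heterosexually active | No conflict |

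1. **Hormonal methods.** Section 10.1.6 advises non-hormonal contraception, while J lists hormonal methods. J's own reason for requiring two methods is that the drug may weaken the hormonal one. If it does, the second method stands alone although J asks for two highly effective ones. Appendix F points the same way: it lists estrogens and medroxyprogesterone as CYP3A4 substrates, and Section 7.5.3 puts 3A substrates at least in the use-with-caution group.
2. **Men.** J sets no number of methods and offers single methods as examples. F sets two. Condom use alone is the clear case. A vasectomized man may fall outside F, but the protocol does not define reproductive potential.
3. **Vasectomized partner.** The woman herself remains of reproductive potential, so F applies to her. Even if the partner's vasectomy counted as one method, F would still call for a second.
4. **After the last dose.** The 6-month period for women agrees. The standard does not: two highly effective methods in J, abstinence or adequate methods in F. Because J covers only heterosexually active women, abstinence itself is not in conflict. The gap lies in the word adequate.
5. **Fetal risk.** G speaks only of missing human information, while Section 10.1.6 gives a general warning. Both can be true, so this is a tension and not a contradiction.
6. **How the rules combine.** Under Section 3.1 both J and F must be satisfied, so the first two subjects in the table are ineligible. On treatment F is the stricter text for them. After treatment J is the stricter text for women. Section 10.1.6 is not an eligibility criterion, so Section 3.1 does not resolve item 1.

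**The case against.** The strongest reply is that nothing is left open. Section 3.1 gives a determinate answer when J is met and F is not: the subject is not eligible. The no-exceptions rule and central checklist review reinforce that. J does not permit a hormonal method on its own, and it adds the second method because of the suspected interaction. Pregnancy tests are scheduled at screening, Cycle 1 and later cycles (Section 6.1), pregnancy ends treatment (Section 8.2), and all pregnancies, including those in partners of male subjects, are reported and followed to outcome (Section 11.4.2).

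Much of this stands. A reader might infer that eligibility or fetal protection is undefined, that subjects may rely on a hormonal method alone, or that G flatly contradicts Section 10.1.6. The documents support none of these, for the reasons just given and because G is limited to human information.

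The reply does not remove the conflicts. If the stricter text always governs, J's wording for men and its vasectomy waiver have no effect, yet they still tell clinicians and subjects something different. The combination rule does not reach the hormonal question. Pregnancy testing detects exposure rather than preventing it, and none is scheduled at end of treatment or in follow-up, when the 6-month period runs.

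**Conclusion.** The point holds as an inconsistency in stated eligibility and safety rules. There are four conflicts (hormonal methods, the requirement for men, the vasectomized-partner waiver, and the post-treatment standard for women) and one tension over fetal risk. The requirements are present but inconsistent, and two people following the text could reach different decisions on the same subject.

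The size cannot be put as a number. A reader might infer that every heterosexually active subject, or a large share of the sample, is affected. The documents give no basis for that, and some method combinations raise none of these conflicts. The primary endpoint, the two-stage design, type I error and power are unaffected.

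The conclusion rests on reading the criteria as written. The eligibility checklist and the consent form are not among the documents reviewed, so how the rules are applied in practice cannot be judged. Nothing here says which contraception rule is right.

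**What to change.** Reconcile Inclusion J (Section 4.2), Exclusions F and G (Section 4.3), Section 10.1.6 and the matching synopsis entries, so that each sex has one set of requirements during treatment and one after the last dose. That text should state:

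- which methods qualify and how many are needed;
- whether hormonal methods count;
- how a vasectomized subject or partner is handled;
- what reproductive potential means for F;
- whether the 90 days for men in J cover contraception as well as sperm donation, since J's sentence ties them clearly only to the latter.

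Replace the statements in G and Section 10.1.6 with a single one that separates what is known in humans from the general warning. Carry the agreed text into the eligibility checklist and the consent form. The choice of rule belongs to the sponsor and investigator. The cost is a wording amendment to the protocol, consent and checklist, with the usual IRB approval. No analysis or sample-size change follows.

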#### 10.1.7 Adverse Event Profile

The most common ( $\geq 20\%$ ) adverse reactions are pain, fatigue, nausea, decreased appetite, vomiting, and constipation.

#### 10.1.8 Drug Interactions

Strong and Moderate Cytochrome P450 (CYP)3A Inhibitors: Avoid coadministration of strong and moderate CYP3A inhibitors with TAZVERIK. Reduce the dose of TAZVERIK if coadministration of moderate CYP3A inhibitors cannot be avoided.

Strong and Moderate CYP3A Inducers: Avoid coadministration with TAZVERIK.

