#### 7.5 Supportive Care and other concomitant therapy

##### 7.5.1 Supportive Care Guidelines

Subjects should receive full supportive care, including transfusions of blood and blood products, antibiotics, antiemetics, antidiarrheals, analgesics, etc., when appropriate. Bisphosphonates or denosumab are allowed for subjects with bone metastases.

Growth factors that support platelet or white cell number or function can only be administered for culture proven bacteremia or invasive fungal infection when approved by the Principal Investigator.

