#### 7.5.3 Prohibited Concomitant Therapy

Supportive care measures consistent with optimal subject care will be permitted throughout the study, as long as the therapy is not included in this section as prohibited.

Subjects are prohibited from receiving the following therapies during the Screening and Treatment Phase of this trial:

- Concurrent cancer therapy, including chemotherapy, radiation therapy, immunotherapy, or biologic therapy may NOT be administered to patients receiving study drug. If these treatments are administered the patient will be removed from protocol therapy.
- Investigational agents other than the study drug in this trial.
- Radiation therapy (allowed if  $\geq$  14 days prior to study registration).
- Cancer-Related Surgery (allowed if  $\geq$  14 days prior to study registration).
- Strong inhibitors and inducers of CYP2C8, CYP2D6, and P-glycoprotein (P-gp) should be used with caution.
- Medications that are sensitive or narrow therapeutic range substrates of CYP3A, CYP2C8, CYP2C9, CYP2C19, CYP2D6 should be avoided if possible. Other substrates of CYP2C8, 2C9, 2C19, 2D6, 3A, P-gp, OATP1B1, OATP1B3, OAT3, MATE1, and MATE2K should be used with caution.
- CYP3A4/5 inhibitors or inducers: Strong CYP3A4/5 inhibitors or inducers are prohibited from 14 days prior to the first dose of Tazemetostat to the end of the study (Appendix F). Note: Dexamethasone for CNS tumors or metastases, on a stable dose, is allowed.
- Live vaccines within 30 days prior to the first dose of trial treatment and while participating in the trial. Examples of live vaccines include, but are not limited to, the following: measles, mumps, rubella, chicken pox, yellow fever, rabies, BCG, and typhoid (oral) vaccine. Seasonal influenza vaccines for injection are generally killed virus vaccines and are allowed. However, intranasal influenza vaccines (e.g. Flu - Mist®) are live attenuated vaccines, and are not allowed. Patients may receive non-live versions of the COVID-19 vaccine.

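### Section 10.1.8's rule on moderate CYP3A inhibitors and inducers, including its dose reduction, is not carried into Sections 7.5.3 and 7.6 or Appendix F

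*Combined protocol and SAP*

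**What the plan says.** Section 10.1.8 (Drug Interactions) sets three rules. On inhibitors: "Avoid coadministration of strong and moderate CYP3A inhibitors with TAZVERIK". On dose: "Reduce the dose of TAZVERIK if coadministration of moderate CYP3A inhibitors cannot be avoided". On inducers: "Strong and Moderate CYP3A Inducers: Avoid coadministration with TAZVERIK". It gives no amount for the reduction.

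Section 7.5.3 (Prohibited Concomitant Therapy) has a narrower CYP3A rule: "Strong CYP3A4/5 inhibitors or inducers are prohibited from 14 days prior to the first dose of Tazemetostat to the end of the study". Exclusion A in Section 4.3 is likewise limited to strong agents. The opening of 7.5.3 permits supportive care "as long as the therapy is not included in this section as prohibited". The section also has milder grades of restriction for other interactions, for example "Strong inhibitors and inducers of CYP2C8, CYP2D6, and P-glycoprotein (P-gp) should be used with caution", and a separate item on drugs that are substrates of CYP3A and other enzymes or transporters.

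Section 7.6 and Table 3 govern dose changes, and toxicity is the only trigger. Appendix F gives moderate CYP3A4 inhibitors and moderate inducers a column each, with no instruction on what to do about them. Section 7.5.3 cites Appendix F only for the strong agents.

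**The concern.** A site decides on concomitant medication and dose from Section 7. Read alone, Section 7 lets a subject stay on full-dose tazemetostat with a moderate CYP3A inhibitor, or start a moderate inducer, although the drug-information chapter says otherwise.

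The situation is foreseeable. Section 7.5.1 says: "Subjects should receive full supportive care, including transfusions of blood and blood products, antibiotics, antiemetics, antidiarrheals, analgesics, etc., when appropriate". Section 10.1.7 states that the most common "adverse reactions are pain, fatigue, nausea, decreased appetite, vomiting, and constipation". By usual drug class (an assumption, since the documents do not classify most of them), the moderate columns of Appendix F include an antiemetic (aprepitant) and anti-infectives such as erythromycin and fluconazole. Section 7.5.2 has concomitant medication documented at each visit, so the drug would be recorded. Section 7 would still not say whether to stop it or what tazemetostat dose to give with it.

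At stake are consistent dosing and subject safety.

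**Working it through.** The point rests on text and a count. There is no design figure to reproduce.

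**1. The sections side by side**

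| Item | Section 10.1.8 | Operative sections |
|---|---|---|
| Strong inhibitors and inducers | Avoid | Prohibited (7.5.3); excluded at entry (4.3 A) |
| Moderate inhibitors | Avoid; if unavoidable, reduce tazemetostat | Not named as a class in 7.5.3; listed without action in Appendix F |
| Moderate inducers | Avoid | Not named as a class in 7.5.3; listed without action in Appendix F |
| Reduced dose for an interaction | Required, amount not stated | None; 7.6 and Table 3 cover toxicity only |

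**2. How many listed agents are affected**

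- Moderate columns of Appendix F: 15 inhibitors + 7 inducers = 22 entries.
- Less 4 anti-cancer drugs (crizotinib, imatinib, nilotinib, dabrafenib), already barred as concurrent cancer therapy.
- Less 2 grapefruit entries, which are also in the strong column and which the diaries tell subjects to avoid.
- Remaining: 22 − 4 − 2 = 16, made up of 10 inhibitors and 6 inducers.

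Appendix F says that it is not exhaustive, so 16 counts what is printed there and is not a ceiling.

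**3. What Section 7 already says about those 16**

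Section 7.5.3 asks sites to avoid sensitive or narrow-range CYP3A substrates where possible, and to be careful with other CYP3A substrates. Checked against the substrate column of Appendix F:

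- Named as substrates (5): aprepitant, conivaptan, dronedarone, isavuconazole, modafinil.
- Reached through a class entry (3): diltiazem and verapamil as calcium channel blockers, and erythromycin as a macrolide.
- Total: 5 + 3 = 8. Conivaptan, dronedarone and isavuconazole are marked sensitive and fall under avoidance. The other five fall under caution.
- Not listed as CYP3A4 substrates (16 − 8 = 8): fluconazole, fosamprenavir, mifepristone, bosentan, efavirenz, etravirine, nafcillin (read from a variant spelling) and rifapentine. Five of these are inducers.

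A substrate rule looks at what tazemetostat does to the other drug. Section 10.1.8 looks at what the other drug does to tazemetostat. The substrate item therefore gives the first eight a reason for care but no tazemetostat dose, and it does not reach the second eight.

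**4. Whether the dose step in 7.6 can stand in**

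The step is 0.75 × 800 = 600 mg twice daily for adults and 0.75 × 520 = 390 mg/m² twice daily for those under 18. It is defined for dose-limiting toxicity and may not be reversed (7.6.2, 7.6.4). A site that borrowed it for a short course of a moderate inhibitor would have no rule for returning to the full dose. Table 3 has only this one reduced level, so no lower dose would be left for a later toxicity.

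**5. Whether Section 7.3 closes the gap**

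Section 7.3 makes the Investigator Brochure and package insert conditions for starting later cycles. It does not cover Cycle 1, and it states no CYP3A rule or dose.

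**The case against.** The best defence is that 10.1.8 is part of the protocol, binds from Cycle 1, and must be followed under Section 14.1. Avoiding and prohibiting can be two tiers: strong agents barred, moderate ones discouraged. Section 7.5.3 permits only supportive measures in keeping with optimal care, 7.5.1 adds that they be appropriate, and 7.5.1 names broad drug classes, not particular agents. The substrate item already prompts care with half of the 16 agents. The package insert, the Investigator Brochure and pharmacy procedures are not available here and may supply the missing dose.

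Most of this stands, and it limits the point. A reader might infer that 7.5.3 contradicts 10.1.8, or that Section 7 is silent on all 16 agents. The documents support neither. The defence does not explain why 7.5.3, which already uses milder grades of restriction for other interactions, leaves moderate CYP3A inhibitors and inducers out of all of them. Nor does it supply the dose that 10.1.8 requires.

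A reader might also try to size the problem from nausea. Section 1.4.1 reports it in 13 of 64 phase 1 patients, and 29 × 13/64 = 5.9. That figure would count subjects with nausea, not subjects given a moderate CYP3A agent. The phase 1 events were usually grade 1 or 2 and came from doses of 100 to 1600 mg twice daily. An antiemetic need not be a moderate agent: ondansetron appears in Appendix F only as a substrate. The figure does not measure this gap.

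**Conclusion.** The point holds as a minor safety-consistency correction. A rule stated in 10.1.8 has no counterpart in the sections that govern concomitant medication and dose, and the reduction it calls for is not quantified anywhere in the protocol. On the printed list, 16 moderate agents have no rule in Section 7 for their effect on tazemetostat, and 8 of those have no CYP3A instruction there at all.

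The counts rest on Appendix F as printed and on ordinary drug classes for diltiazem, verapamil and erythromycin. The number of subjects who would receive a moderate agent, the change in tazemetostat exposure and any resulting toxicity cannot be derived from the documents. A reader might infer that altered exposure would bias the response rate or disturb the two-stage design. Nothing in the documents supports that.

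**What to change.** - **Section 7.5.3:** state that moderate CYP3A inducers are to be avoided, and that moderate CYP3A inhibitors are to be avoided or, if that is impossible, used only with a reduced tazemetostat dose. Refer to 10.1.8 and to the moderate columns of Appendix F.
- **Section 7.6:** add an interaction-based reduction separate from the toxicity step. Take its amount, and the rule for returning to the prior dose once the inhibitor stops, from the package insert or Investigator Brochure. State it for both the adult flat dose and the mg/m² dose, because the trial enrols from age 12 while the labelled sarcoma indication in 10.1.1 starts at 16.
- **Exclusion A:** leave unchanged. Section 4 allows no exceptions, 10.1.8 itself tolerates a moderate inhibitor with a lower dose, and a wider exclusion could turn away patients with a rare disease.

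The cost is one wording amendment, with IRB approval and SRMC submission as applicable (Section 14.7), and some substitutions of concomitant drugs. No new data collection is needed, because medications are already documented at each visit. Eligibility and the statistical design do not change.
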